5.1.2.3 Sitravatinib Dose Modification and Discontinuation

In the event of adverse events attributed to sitravatinib and deemed intolerable by the Investigator, treatment should be either temporarily or permanently discontinued. For patients who temporarily discontinue treatment, treatment may resume following resolution of treatment-related adverse events to Grade 1 or baseline with the administration of sitravatinib at a reduced dose level as outlined in Table 9. Once the dose has been reduced, re-escalation is generally not recommended but may be

considered on a case-by-case basis. If the administration of sitravatinib is interrupted for reasons other than toxicity, then treatment with the study drug may be resumed at the same dose.

Table 9: Sitravatinib Free Base Formulation Sequential Dose Reductions for Individual Patients

150 mg once daily (eliminated after lead-in evaluation)

120 mg once daily

80 mg once daily

60 mg once daily*

Sitravatinib Malate Direct Blend Formulation Sequential Dose Reductions for Individual Patients

60 mg once daily 40 mg once daily

Sitravatinib Malate Roller Compaction Formulation Sequential Dose Reductions for Individual Patients

100 mg once daily 80 mg once daily 60 mg once daily

40 mg once daily

A two-step dose reduction (e.g. 100 mg to 60 mg once daily) is permitted at the discretion of the investigator

In the event of sitravatinib-related AE, dose reduction with continuous treatment is preferred over repeated dose interruption. Following sitravatinib dose reduction and control of adverse event, re-challenge at a higher sitravatinib dose is permitted at the discretion of the Investigator. If treatment with sitravatinib is withheld for ≥ 28 consecutive days, then permanent discontinuation from this study drug should be considered. If one study drug is interrupted or discontinued, administration of the other study drug may continue at the discretion of the Investigator.

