8.4 Reporting of SAEs and AEs

8.4.1 Reporting Period

The active reporting period for SAEs begins from the time that the patient provides informed consent (i.e., prior to undergoing any study-specific procedure or assessment) and continues until 28 days post last administration of either therapy. All SAEs will be followed until the event has resolved or stabilized to a chronic condition, whichever is later. Death must be reported if it occurs during the active reporting period for SAEs regardless of whether a subsequent anticancer therapy is administered. Serious adverse events occurring to a patient after the active reporting period has ended should be reported to the Sponsor if the Investigator becomes aware of them and if the Investigator assesses at least a reasonable possibility of being related to study drug.

The reporting period for non-serious AEs begins from the day of first dose of study treatment and continues until at least 28 days after last administration of study treatment and/or until recovery from all acute toxicities associated with the drug administration to a chronic condition, whichever is later. If a patient begins a subsequent anticancer therapy, the AE reporting period ends at the time the new treatment is started.

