4.2 Study Treatment Definitions

4.2.1 Study Drug

The investigational agents of primary interest (Glesatinib, Sitravatinib, Mocetinostat) are referred to in the protocol as both study drugs and study treatments. Within the context of this SAP these terms are used interchangeably.

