8.4 Safety Variables

With regard to safety summaries, the term “on-treatment” is the period from first dose until either last dose + 28 days or the start of anti-cancer therapy, whichever is earlier.

AEs, laboratory values and ECGs will be graded according to the NCI CTCAE v4.03 (see Section 13.0 for link to the criteria), ECGs will also be graded according to International Conference on Harmonisation (ICH) E14.

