8.4.1 Adverse Events

8.4.1.1 Treatment-Emergent AEs (TEAEs)

TEAEs are those that first occur or increase in severity after the first dose of study treatment and not more than 28 days after the last dose of study treatment and prior to the initiation of subsequent anti-cancer therapy. Any ongoing TEAE (or any baseline sign/symptom recorded as part of Medical History) that changes in attribution or increases in severity is captured as a new AE.

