11.1.7.2 Treatment Emergent Adverse Events (TEAEs)

All AEs will be coded according to the Medical Dictionary for Regulatory Activities (MedDRA) v19.0 dictionary by SOC, PT, and severity grade using NCI CTCAE v4.03.

An overall summary of TEAEs will be presented, with supporting tables summarizing TEAEs by SOC and PT, as well as PT only. Counts will be presented by patient rather than event and those experiencing multiple instances of the same event will be counted only once within each SOC or PT.

The following summaries will be presented by SOC and PT for the Sitravatinib plus Nivolumab treatment arm, using the Safety Population, unless otherwise specified.

- Any TEAEs
- Any DLTs (DLT Evaluable Population)
- Any Treatment-Related TEAEs
- Any Nivolumab-Related TEAEs
- Any Sitravatinib-Related TEAEs
- Any TEAE leading to dose reduction or interruption of either study drug
- Any Treatment-Related TEAE leading to dose reduction or interruption of either study drug
- Any TEAE leading to drug discontinuation of either study drug
- Any TEAE leading to Nivolumab discontinuation
- Any TEAE leading to Sitravatinib discontinuation
- Any Treatment-Related TEAE leading to drug discontinuation of either study drug
- Any Nivolumab-Related TEAE leading to Nivolumab discontinuation
- Any Sitravatinib-Related TEAE leading to Sitravatinib discontinuation
- Any TEAE leading to study discontinuation
- Any TEAEs by Maximum CTCAE Grade
- Any Treatment-Related TEAEs by Maximum CTCAE Grade
- Any Nivolumab-Related TEAEs by Maximum CTCAE Grade
- Any Sitravatinib-Related TEAEs by Maximum CTCAE Grade
- Any irAEs

- Any AESIs (if at least one AESI is identified)

For the Glesatinib and Nivolumab treatment arm, a single summary table by SOC and PT will be presented.

- Any Glesatinib-Related TEAEs

In addition to the SOC and PT summaries, the following summaries will also be presented by PT only for the Sitravatinib plus Nivolumab treatment arm

- Any TEAEs
- Any TEAEs by Maximum CTCAE Grade (Any Grade, Grade 3, Grade 4, Grade 5)
- Any Treatment-Related TEAEs by Maximum CTCAE Grade (Any Grade, Grade 3, Grade 4, Grade 5)
- Any Nivolumab-Related TEAEs by Maximum CTCAE Grade (Any Grade, Grade 3, Grade 4, Grade 5)
- Any Sitravatinib-Related TEAEs by Maximum CTCAE Grade (Any Grade, Grade 3, Grade 4, Grade 5)

All TEAEs will be listed, separate listings for irAEs and TEAEs leading to study drug discontinuation (TEAEs and related TEAEs) will also be presented.

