where on-treatment is defined as the period of time after the first dose of study treatment and not more than 28 days after the last dose of study treatment and prior to the initiation of subsequent systemic anti-cancer therapy.

All echocardiogram results will be listed.

Pregnancy Test

For patients of childbearing potential, a serum or urine pregnancy test will be performed at screening. Pregnancy tests will also be done whenever pregnancy is suspected during the study. Additional pregnancy testing may be necessary if required by local practices or regulations. Pregnancy testing data will be listed for the Safety Population.

Long Term Follow-up and Death

Long term follow-up, inclusive of survival status, follow-up anti-cancer therapies and causes of death will be presented in separate listings.

Biomarkers

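### The SAP does not say which drug's last dose closes the TEAE window, and its own definition of study treatment would close it on sitravatinib while nivolumab continues

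*SAP*

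**What the plan says.** - **SAP 4.2.1**, under the heading Study Treatment Definitions: "The investigational agents of primary interest (Glesatinib, Sitravatinib, Mocetinostat) are referred to in the protocol as both study drugs and study treatments". It adds: "Within the context of this SAP these terms are used interchangeably". SAP 4.2.2 gives the combination with nivolumab a different name, *treatment arm*.
- **SAP 8.4.1.1** closes the TEAE window "not more than 28 days after the last dose of study treatment and prior to the initiation of subsequent anti-cancer therapy".
- **SAP 11.1.7.6** repeats this for the on-treatment LVEF decreases: "not more than 28 days after the last dose of study treatment".
- **SAP 8.4**, the general on-treatment definition for safety summaries, "is the period from first dose until either last dose + 28 days or the start of anti-cancer therapy, whichever is earlier". It names no drug.
- **SAP 8.4.1.2** runs SAE reporting to at least 28 days after study treatment, again without naming a drug.
- **Protocol 8.4.1** is explicit for SAEs: reporting "continues until 28 days post last administration of either therapy". SAP Table 1 footnote 14 likewise runs SAE reporting from the investigational agent or nivolumab.
- **Protocol 5.1.2.3**: "If one study drug is interrupted or discontinued, administration of the other study drug may continue at the discretion of the Investigator".

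**The concern.** The TEAE window depends on a term that the SAP's definitions section attaches to the investigational agent, in a trial where the partner drug may be given alone for an open-ended period. A programmer who follows 4.2.1 would take the last sitravatinib date as the anchor. A programmer who follows the usage in 8.3.1 or 11.1.7.2 would take the later of the two last doses. The two would produce different tables from the same data.

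Safety and tolerability of the combination is a secondary objective. The events at risk occur on nivolumab after sitravatinib has been stopped. They include nivolumab-related TEAEs, TEAEs leading to nivolumab discontinuation, treatment-emergent SAEs and TEAEs with a fatal outcome.

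**Working it through.** The plan gives no figure to reproduce. The check compares definitions and then works through the dates.

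**1. What the terms cover**

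| Place | Usage |
|---|---|
| SAP 4.2.1 | Both terms attached to the investigational agents |
| SAP 7.4, 8.3.3 | Nivolumab named separately, beside the study drug |
| SAP 8.3 | Study drug limited to glesatinib and sitravatinib, for the exposure definitions |
| SAP 8.3.1 | Study treatment duration reported for each study drug and for nivolumab, so the term includes nivolumab |
| SAP 11.1.7.2 | "Any TEAE leading to drug discontinuation of either study drug", planned for the sitravatinib plus nivolumab arm, so nivolumab counts as a study drug |
| SAP 8.4, 8.4.1.1, 8.4.1.2, 11.1.7.6 | No drug named |

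The usage is inconsistent, and the window sections do not settle it.

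**2. Size of the difference**

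Let S be the day of the last sitravatinib dose and N the day of the last nivolumab dose, with no subsequent anti-cancer therapy before either window closes.

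- Window end under 4.2.1: S + 28.
- Window end counting either agent: max(S, N) + 28.
- Difference: max(0, N − S).
- Days between the last two doses that fall outside the 4.2.1 window: max(0, N − S − 28).

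If sitravatinib outlasts nivolumab, the two readings agree. The 4.2.1 reading can therefore only shorten the window. The Safety Population denominator does not change, so incidence can only fall.

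The documents give no values for N − S. Assumed values:

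| N − S (days) | Window shortened by | Nivolumab-period days uncounted | Share of nivolumab-alone period |
|---|---|---|---|
| 28 | 28 | 0 | 0% |
| 84 | 84 | 56 | 56/84 = 67% |
| 168 | 168 | 140 | 140/168 = 83% |
| 182 | 182 | 154 | 154/182 = 85% |

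**3. Would events be expected there?**

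Take S = Day 56. The 4.2.1 window closes on Day 56 + 28 = 84, which is 84/30.4375 = 2.76 months. Protocol 1.7.3.3 gives these median onsets for single-agent nivolumab:

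- before the close: hyperthyroidism 1.5 months;
- about at the close: rash 2.8, hypothyroidism 2.9;
- after the close: hepatitis 3.3, pneumonitis 3.5, adrenal insufficiency 4.3, nephritis 4.6, hypophysitis 4.9, colitis 5.3.

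Protocol 5.1.4.2.2 gives a colitis median of 2.7 months in NSCLC patients alone, which is also about at the close. Onset after the close is plausible for several event types. These medians do not give the proportion lost in this trial.

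**4. Which outputs are reached**

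- Reached under the 4.2.1 reading: the TEAE tables in 11.1.7.2, the treatment-emergent SAE and fatal TEAE tables in 11.1.7.3, and the LVEF decrease categories in 11.1.7.6.
- Undetermined: summaries that rely on 8.4, which says only *last dose*. The irAE and AESI definitions carry no dosing cut-off, but SAP 11.0 restricts safety summaries to the 8.4 period.
- Not reached: DLTs, which are confined to Cycle 1, and the death count in the disposition table (11.1.1).

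**The case against.** The best defence is that the intended reading is already clear. SAP 4.2.1 describes what the protocol calls the investigational agents and never says that nivolumab is excluded. SAP 8.3 restricts *study drug* for exposure only, which would be unnecessary if 4.2.1 already did so throughout, and the restriction is not repeated in 8.4. The protocol places nivolumab under Study Treatments and heads its section as a study drug. SAP 4.1, which lists changes from the protocol, mentions no narrowing of the safety window. Planned tables of nivolumab-related TEAEs fit poorly with a window driven by sitravatinib alone.

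Most of this stands as evidence of intent. It does not remove the problem, because the one place headed as a definition points the other way and the window sections name no drug.

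A reader might go further and infer three things that the documents do not support:

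- **That the SAP firmly excludes nivolumab.** It does not, since 8.3.1 and 11.1.7.2 include it.
- **That every safety table loses events.** DLTs and disposition deaths do not, and the 8.4 summaries are undetermined.
- **That the events vanish from listings.** SAP 11.1.7.2 and 11.1.7.3 mention listings of treatment-emergent events, but 11.0 promises listings of all collected data unless otherwise specified, so this loss is uncertain.

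It would also be wrong to conclude that at least half of each immune-related event type would be missed. The Day 56 patient is assumed, the medians come from single-agent nivolumab patients who had the event, and some of them fall inside or near the window.

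**Conclusion.** The SAP leaves open which last dose closes the TEAE and LVEF windows. The definition it does supply, applied as written, gives a window that conflicts with the SAE period in Protocol 8.4.1 and in SAP Table 1 footnote 14. Under that reading the window is shortened by N − S for every patient whose nivolumab outlasts sitravatinib, and the error runs only toward a safer-looking combination. A Safety Population patient who received nivolumab alone would, on the same reading, have no TEAE window.

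The conclusion rests on two assumptions: that some patients continue nivolumab alone for more than 28 days, and that the derivation follows 4.2.1. The protocol permits the first, but the documents do not say how many patients this is, so the number of events lost cannot be stated. The point should be settled before database lock, because it bears on a secondary objective and two competent programmers could reach different tables.

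**What to change.** In SAP 8.4, 8.4.1.1, 8.4.1.2 and 11.1.7.6, state that the window opens at the first dose of either the investigational agent or nivolumab. State that it closes 28 days after the later of the last investigational-agent dose and the last nivolumab dose. Keep the existing cut-off at the start of subsequent anti-cancer therapy where it applies. Limit the 4.2.1 definition to the exposure sections, as 8.3 already does.

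The cost is a wording change and one line of derivation code, and SAP 4.0 provides for a final version before lock. More events will be counted as treatment-emergent. For SAEs the protocol already collects the data to the later date. For non-serious events Protocol 8.4.1 uses the same unnamed term, so confirm that sites recorded these to the later of the two dates.

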8.4.1.2 Serious Adverse Events (SAEs)

Serious adverse events (SAEs) are reported from the time that the patient provides informed consent (i.e., prior to undergoing any study-specific procedure or assessment) until at least 28 days after last administration of study treatment. All SAEs ongoing 28 days after the last dose should be followed until resolution, stabilization to a chronic condition or administration of alternative cancer treatment, whichever occurs first.

8.4.2 Immune-Related Adverse Event (irAE)

An irAE is defined as an AE that is associated with drug exposure and is consistent with an immune-mediated mechanism of action and where there is no clear alternate etiology. irAEs will be identified by the Investigator on the adverse events CRF page.

8.4.3 Adverse Events of Special Interest (AESI)

An AESI is defined as an AE of scientific and medical interest specific to understanding of the Investigational Product and may require close monitoring and rapid communication by the Investigator to the sponsor. AESIs will be identified by the medical team based on coded terms.

8.4.4 Physical Examinations

A physical examination including all major body systems is mandated at Screening and End of Treatment Visits only. During study treatment, symptom directed physical examinations are performed.

8.4.5 Vital Signs

Vital signs: systolic and diastolic blood pressure, pulse rate, respiratory rate, body temperature, height and weight. Height will be recorded at screening only.

8.4.6 Clinical Laboratory Assessments

Clinical laboratory parameters to be collected routinely for hematology, chemistry, urinalysis and thyroid function are listed in Table 6 in Section 11.1.7.4 .

Pregnancy Testing: For patients of childbearing potential, a serum or urine pregnancy test will be performed by the local laboratory at screening. Pregnancy tests will also be done whenever pregnancy is suspected during the study.

8.4.7 Electrocardiograms

Single and triplicate 12-Lead ECG parameters will be collected as shown in Table 1-4. Assessments include rhythm, heart rate, PR, QRS, QT and RR, the QT interval will be corrected for heart rate using Fridericia's formula (QTcF). The Investigator's overall interpretation will also be collected.

The baseline to be used in the calculation of changes over time will be the mean of the 6 pre-dose values, i.e., the triplicate values at Cycle 1 Day 1 (-1 hour and -0.5 hours pre-dose). If any of the 6 values are missing, the mean will be calculated using the observed values.

8.4.8 Echocardiograms

Echocardiograms will be performed in the Sitravatinib treatment arm at screening, and thereafter as shown in Table 1. Additional assessments of left ventricular ejection fraction (LVEF) and evaluation of pericardial effusions may be

performed as clinically indicated at the Investigator's discretion if there are signs or symptoms of cardiotoxicity. Where abnormalities indicating pericardial effusion exist, weekly assessments will be performed until normalization as described in Section 5.1.3.4.1 of the protocol.

8.4.9 Prior and Concomitant Medications

Medications administered to study participants are captured on a log CRF page.

Medications are considered prior medications if they have a start date prior to the date of first dose of study medication or a partial start date which indicates the medication was begun prior to the first dose of study treatment. Medications with missing start dates will be considered both prior and concomitant medications, unless the end date is prior to first dose, in which case it would be considered prior only.

Medications with a missing start date but an observed end date after first dose of study treatment, will be considered as concomitant medication.

Concomitant medications are defined as medications administered to study participants on or after the first dose of study treatment, or a prior medication with an end date after the first dose of study treatment.

A medication can be considered both prior and concomitant.

8.5 Predetermined Covariates and Prognostic Factors

Enrollment into each treatment arm of the CIT-experienced patients will be stratified by prior outcome of treatment with a checkpoint inhibitor (prior clinical benefit, no prior clinical benefit). Each combination of treatment arm and prior clinical benefit stratum, including overall, will be analyzed separately.

Enrollment into each treatment arm of the CIT-naïve patients will be stratified according to the patient's PD-L1 status (No/Low, High). Each combination of treatment arm and PD-L1 status, including overall, will be analyzed separately.

9.0 Data Handling

9.1 Missing Dates

9.1.1 Imputation of Partial Adverse Event or Medication Dates

The rules to impute missing start and stop dates will be applied as follows:

Start Date

If the start date is completely missing (i.e., the day, month, and year are all unknown) the start date will not be imputed.

Missing Day Only

- If the month and year of the incomplete date are the same as the month and year of the first dose date, then the day of the first dose date will be assigned to the missing day.
- If either the year is before the year of the first dose date or if years are the same but the month is before the month of the first dose date, then the last day of the month will be assigned to the missing day.
- If either the year is after the year of the first dose date or if both years are the same but the month is after the month of the first dose date, then the first day of the month will be assigned to the missing day.

Missing Month Only

- The day will be treated as also missing and both month and day will be replaced according to the below procedure.

Missing Day and Month

- If the year of the incomplete date is the same as the year of the first dose date, then the day and month of the first dose date will be assigned to the missing fields.
- If the year of the incomplete date is not the same as the year of the first dose date, then January 1 will be assigned to the missing fields.
- If the stop date is complete and the imputed start date is after the stop date, then the start date will be imputed using the stop date.

Stop Date

Missing Day Only

- If the month and year of the incomplete date are the same as the month and year of the last visit date, then the day of the last visit date will be assigned to the missing day.
- If either the year is before the year of the last visit date or if both years are the same but the month is before the month of the last visit date, then the last day of the month will be assigned to the missing day.
- If either the year is after the year of the last visit date or if both years are the same but the month is after the month of the last visit date, then the first day of the month will be assigned to the missing day.

Missing Month Only

- The day will be treated as missing and both month and day will be replaced according to the below procedure.

Missing Day and Month

- If the year of the incomplete date is the same as the year of the last visit date, then the day and month of the last visit date will be assigned to the missing fields.
- If the year of the incomplete date is before the year of the last visit date, then December 31 will be assigned to the missing fields.
- If the year of the incomplete date is after the year of the last visit date, then January 01 will be assigned to the missing fields.

9.1.2 Imputation of Partial Subsequent Anti-Cancer Therapy Dates

The following rules will be applied to impute missing subsequent anti-cancer therapy dates.

Missing Day Only

- If the month and year of the incomplete date are the same as the month and year of the last dose date, then the last dose date + 1 will be assigned to the missing day.
- If the month and year of the incomplete date are after the month and year of the last dose date, then the first day of the month will be assigned to the missing day.

Missing Month Only

- The day will be set as missing and treated as missing Day and Month.

Missing Day and Month

- If the year of the incomplete date is the same as the year of the last dose date, then the last dose date + 1 will be assigned to the missing day and month.
- If the year of the incomplete date is after the year of the last dose date, then January 01 will be assigned to the missing fields.

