7.1 Efficacy

All patients enrolled in the study are to be evaluated for disease activity as outlined in the Schedule of Assessments (Table 1). Screening/baseline tumor assessments should include CT or MRI of the chest, abdomen, and pelvis, whole body bone scan, MRI of the brain and evaluation of any superficial lesions. On-study assessments will include all known and suspected sites of disease and will be performed at 8-week intervals until approximately 1-year and then every 16 weeks; bone scans may be performed half as often as other radiology evaluations (i.e., every 16 weeks). The allowable windows for assessments are 4 weeks prior to first study treatment for screening/baseline assessments and ± 10 days for on-study disease assessments. All known and suspected sites of disease

should be evaluated at each assessment. Assessments will be performed until objective disease progression is documented or subsequent anti-cancer therapy is begun.

CT scans should be performed with contrast agents unless contraindicated for medical reasons. If intravenous contrast is medically contraindicated, the imaging modality to be used (either CT without contrast or MRI) should be the modality which best evaluates the disease, and the choice should be determined by the Investigator in conjunction with the local radiologist. Depending on the adequacy for evaluation of disease, a combination of CT without contrast and MRI should most often be used. CT without contrast is preferred for evaluation of lesions in lung parenchyma. MRI is not adequate for evaluation of lung parenchyma but should also be performed to evaluate all other aspects of the chest. MRI of the abdomen and pelvis should substitute for CT with contrast unless the method does not adequately depict the individual's disease, in which case CT without contrast is preferred.

For patients having effusions or ascites, cytological proof of malignancy should be obtained prior to selection of the effusion as a non-target lesion. Effusions that have not been evaluated using cytology or were found to be non-malignant should not be considered to be cancer lesions.

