9.4.4 Progression Free Survival

Progression-free survival (PFS) is defined as the time from date of first study treatment to first PD or death due to any cause in the absence of documented PD. Censoring for the PFS endpoint will be assigned on the date of the last tumor assessment if no assessment of tumor progression is identified and the patient does not die while on study. For patients in whom two or more sequential assessments are missed, followed by the finding of tumor progression, the PFS endpoint will be censored on the date of the last tumor assessment before the gap. Patients lacking an evaluation of disease after first study treatment will have their PFS time censored on the date of first dose with duration of 1 day. Patients who start a new anti-cancer therapy prior to documented PD will have the endpoint censored at the date of the last tumor assessment prior to the start of the new

therapy. The Kaplan-Meier method will be used to obtain the estimate of median progression-free survival time.

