8.2.1 Objective Response Rate (ORR)

Objective disease response will be categorized in accordance with RECIST v1.1. ORR is defined as the proportion of patients documented to have a confirmed CR or PR. ORR as reported by the investigator will be used in decision making for study expansion (Predictive Probability Design).

Best Overall Response (BOR) is defined as the best response among all overall responses (in the order CR, PR, SD, PD then NE) recorded from the start of study drug until disease progression/recurrence or start of subsequent anti-cancer therapy, whichever comes first. The status of best response of CR or PR must be confirmed by repeat tumor assessment within no less than 4 weeks according to RECIST v1.1. If the status of CR or PR cannot be confirmed by repeat tumor assessment, the BOR of unconfirmed CR and PR will be SD or NE. The status of BOR of SD requires an on-study assessment after at least 42 days from first dose date of treatment.

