11.1.6.2.3 Progression-Free Survival (PFS)

PFS will be summarized in the same manner as DoR, though conducted using the FAS. In addition, the PFS rate at 3, 6 and 9 months will be analyzed using KM methodology (Greenwood's formula, Kalbfleisch and Prentice, 1980).

Censoring Rules for PFS

- Event time will be censored on the date of first dose with duration of 1 day for;
 - No Disease Assessments Performed On-Study
i.e. Patients lacking evaluation of disease after first study treatment, unless they die within 2 tumor assessments of baseline (on or prior to week 16, i.e. Cycle 5 Day 1 plus the 10 day window, which is Study Day 122), then they will be treated as experiencing an event with date of death as the event date.
 - Patients with baseline or post-baseline assessments inadequate to apply RECIST v1.1 criteria.
- Patients without documented PD will be censored at the date of the last evaluable tumor assessment prior to the start of the new therapy (if received any), unless they die within 122 days of last evaluable tumor assessment, in which case they will be assessed as having an event on the date of death.

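### SAP 9.1.2 dates a partly recorded new therapy to the earliest possible day without checking scan dates, so a true confirming scan can be cut out of the primary ORR

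*SAP*

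**What the plan says.** SAP 9.1.2 gives four outcomes for a partial subsequent-therapy date:

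- Day missing, same month as last dose: "then the last dose date + 1 will be assigned to the missing day".
- Day missing, later month: "then the first day of the month will be assigned to the missing day".
- Day and month missing, same year as last dose: "then the last dose date + 1 will be assigned to the missing day and month".
- Day and month missing, later year: "then January 01 will be assigned to the missing fields".

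The last dose date is the only other date consulted.

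The imputed date feeds the efficacy derivations. SAP 8.2.1 takes best overall response from assessments "recorded from the start of study drug until disease progression/recurrence or start of subsequent anti-cancer therapy, whichever comes first". It requires CR or PR to be confirmed at least 4 weeks later and counts only confirmed responses in ORR. SAP 11.1.6.2.3 (PFS) states: "Patients without documented PD will be censored at the date of the last evaluable tumor assessment prior to the start of the new therapy". SAP 11.1.6.2.2 (DoR) words its rule the same way.

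Scanning does not stop with study drug. Protocol 7.1: "Assessments will be performed until objective disease progression is documented or subsequent anti-cancer therapy is begun".

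**The concern.** The rule can only err early, and it ignores information already in the database. Because protocol 7.1 ends study scans once new therapy begins, a study scan dated after the imputed start is evidence that therapy had not yet begun on that day. The SAP nevertheless lets the imputed date overrule the scan.

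At stake is the primary endpoint. A patient with PR on two study scans 8 weeks apart can be classified as SD (or NE) because another field was incompletely recorded. The patients exposed are those who stopped study drug before progression and went on to another therapy.

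**Working it through.** **1. The plan's own figures.** For the 9-then-17 design (at least 1, then at least 3 responses; 5% against 30%), the exact two-stage binomial gives early stopping 0.630, type 1 error 0.0466 and power 0.9045, as stated in SAP 6.2.1.2. For 25 responses in 125, Clopper-Pearson gives 13.4-28.1%, as in protocol Table 20. These figures serve only to scale the cost of a lost response.

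**2. Direction and size of the date error.** The four rules were applied to every last-dose day in 2019, with real therapy starts 1 to 719 days later. The imputed date was never later than the real one. The largest shift was 30 days with the day missing, and 364 days (365 in a leap year) with day and month missing.

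**3. Two worked records (dates assumed).** Both have first dose 4 Jan 2019, PR 1 Mar (day 57), last dose 10 Mar and confirming PR 26 Apr (day 113).

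*Case A, year only.* PD is on 21 Jun (day 169). New therapy starts 1 Jul, recorded as 2019.

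- Imputed start: 11 Mar. The 26 Apr scan falls outside the window.
- BOR: confirmed PR becomes SD. The patient leaves ORR and the DoR subset.
- PFS under the SAP wording: still an event, 169/30.4375 = 5.55 months.
- PFS if protocol 9.4.4 is applied instead: censored on 1 Mar, 57/30.4375 = 1.87 months.

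*Case B, day missing.* No PD. New therapy starts 29 Apr, recorded as Apr 2019.

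- Imputed start: 1 Apr. The 26 Apr scan is again outside the window, so BOR becomes SD.
- PFS censoring moves from 113/30.4375 = 3.71 months to 1.87 months.
- DoR should be censored at (56+1)/30.4375 = 1.87 months from first response. Instead the patient is not in the DoR analysis.

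Case B shows that the ORR loss is not confined to year-only dates. It can also occur when a patient changes therapy without PD in the same month as the confirming scan.

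**4. How often a vulnerable record is affected.** A simulation took responders who stopped drug between first PR and the confirming scan. It assumed scans every 8 weeks ±10 days, PD at week 24, 32 or 40, and therapy 7-42 days after PD. With year-only dates about 62% lost the confirming scan. With only the day missing none did, because in that set-up therapy always follows PD; case B lies outside it.

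**5. Expected number.** The documents give no rate of partial dates. Assume that 5-20% of patients stop drug before PD and that 5-20% of their therapy dates are partial: 0.05×0.05 = 0.0025 to 0.20×0.20 = 0.04. Take an ORR of 20% (25 of 125). Assume generously that every early stop falls in the vulnerable window and every partial date is year-only.

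- 125 patients: 25×0.0025×0.62 = 0.04 to 25×0.04×0.62 = 0.62 responders lost. If every such record lost its confirmation, the upper end is 25×0.04 = 1.0.
- 17 patients at 30% ORR: 17×0.30×0.04×0.62 = 0.13 at the upper end.

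**6. What one lost responder does.**

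- 17 patients, H0 5%: P(X≥4) = 0.0088 and P(X≥3) = 0.0503. The test in SAP 11.1.6.1 uses one-sided 0.025.
- 125 patients: 25 to 24 responses moves ORR from 20.0% (13.4-28.1) to 19.2% (12.7-27.2).

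**The case against.** The strongest reply has four parts.

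*Progressions are not lost.* A reader might infer that PD scans falling after the imputed start drop out of DoR and PFS, so that documented progressions become censorings. The SAP does not support this: its new-therapy cut-off in 11.1.6.2.2 and 11.1.6.2.3 is limited to patients without documented PD. For PFS the effect needs protocol 9.4.4, which says "Patients who start a new anti-cancer therapy prior to documented PD will have the endpoint censored". Protocol 9.2 leaves the detailed censoring rules to the SAP, and protocol 9.4.3 has no new-therapy censoring for DoR. This part of the reply stands. What remains is that SAP 4.1 lists no change to protocol 9.4.4, so the two documents differ without explanation.

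*The case is rare.* Subsequent therapies are collected every 2 months (±14 days), so a year-only date should be unusual, and the patient must also be a responder who stopped at the wrong moment. This stands. A reader might multiply 125 by 4% and expect up to 5 affected patients; that ignores responder status and timing.

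*The rule is conservative for ORR.* Early imputation cannot create a responder, 3/17 still meets the design's criterion for further investigation, and expansion may start from unconfirmed responses. All true, but the SAP also plans an exact test and interval on confirmed ORR in each stratum, and those would be wrong for the affected patient.

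*A later scan is not proof.* A site might scan after new therapy despite protocol 7.1, and moving the date later could then admit a response to that therapy. This is a real but small cost, and the reason to retain the present rule as a sensitivity analysis.

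**Conclusion.** The point holds for confirmed ORR, for membership of the DoR subset, and for the DoR and PFS censoring dates of patients without documented PD. The imputation always errs early and disregards scans that show therapy had probably not begun. It does not turn documented progressions into censorings under the SAP as written; that would follow for PFS only if protocol 9.4.4 governed.

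The number affected is unknown and probably small: likely under one patient in the 125-patient cohort on the assumed rates above, where a single loss moves ORR by 0.8 points (20.0% to 19.2%). The consequence is material mainly in the 17-patient strata, which SAP 8.5 analyzes separately and where one responder can decide the test. The 4/17 example is a boundary case chosen to show this, not a forecast.

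**What to change.** In SAP 9.1.2, for efficacy derivations, impute the therapy start as the later of the current rule's date and the day after the last on-study tumor assessment (counting assessments up to and including the PD assessment), capped at the last day of the recorded month or year. Use that date in SAP 8.2.1, 11.1.6.2.2 and 11.1.6.2.3. In case A it gives 22 Jun and in case B 27 Apr; both restore the confirmed PR, and case B is again censored on 26 Apr.

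Keep the current earliest-date rule as a sensitivity analysis for ORR. Separately, reconcile SAP 11.1.6.2.3 with protocol 9.4.4 on whether PD after new therapy counts as a PFS event, and record the choice in SAP 4.1.

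The cost is a few sentences and a small programming change, with no new data. SAP 4.0 already provides for a final version before database lock. The downside is that a scan taken shortly after the real therapy start could occasionally be kept; the sensitivity analysis would show whether that matters for ORR.
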